Cover Page

Study Protocol

Study Title: Mirror Therapy and Treadmill Training for Patients with Chronic Stroke. A Pilot Randomised Controlled Trial

Document creation date: December 12th 2014

NCT number [not yet assigned].

Identifiers: [NCT ID not yet assigned]

Study Protocol for Mirror Therapy and Treadmill Training ([name], IT Sligo, Ireland).

Research sessions will take place in the Institute of Technology Sligo, in the health science physiology lab located in the main building on campus. A total of 30 participants will be randomly assigned to one of two conditions.

Patients will verbally guide the speed of the treadmill at the beginning of each of the 12 therapy sessions and this will be adjusted by the therapist accordingly. A COSMED h/p/cosmos T170 treadmill will be for the intervention. Patients encouraged to walk at their comfortable walking velocity when on the treadmill. Treadmill velocity in session will be guided by baseline data from the Ten Metre Walk Test providing an average comfortable walking velocity in metres per second. For safety and the fact that no weight bearing harness will be employed during the intervention, patients will be advised to use the treadmill handrails for support when required. There is a stationary handrail in front of the participant where individual hands or both hands can be placed and individual stationary handrails for single hand placement on the left and right sides. The participant will also be provided with contact-guard assistance throughout each mirror and treadmill session. Patients will be asked to wear dark sports leggings so that the non-paretic leg can be fully viewed by rolling the fabric above the knee joint and the paretic limb is kept completely covered by the sports leggings to assist in appropriate mirror visual feedback of the non-paretic limb.

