Cover Page

Statistical Analysis Plan

Study Title: Mirror Therapy and Treadmill Training for Patients with Chronic Stroke. A Pilot Randomised Controlled Trial

Document creation date: December 12th 2014

NCT number [not yet assigned].

Identifiers: [NCT ID not yet assigned]

Statistical Analysis Plan for Mirror Therapy and Treadmill Training ([name], IT Sligo, Ireland).

All data was analysed using IBM SPSS Statistics 23 for Windows. Conformity to the normal distribution of variables was tested using a combination of the Shapiro-Wilk test and visual assessment (histograms). Demographic characteristics and outcome variables are described as mean ± SD. Groups were compared at baseline using the independent samples t-test for the continuous variables, and the chi-square test for categorical data. Intention-to-treat analysis was used and patients were excluded from a given analysis if their corresponding measurement was missing. The paired samples t-test and the Wilcoxin signed rank test were used to analyse within-subject differences (T1 vs T2 vs T3). Between-subject differences (MT vs PL) were analysed using the independent samples t-test and the Mann-Whitney U test. The interaction of group and time determined the effectiveness of mirror therapy on outcome measures. All tests were conducted on a 5% significance level. Effect sizes for non-parametric tests were calculated using r. Effect sizes for parametric tests were calculated using Cohens's d for within-group analysis and r for between group analysis. Cohens d values of 0.2, 0.5, and 0.8 were interpreted as small, medium, and large respectively; r values of 0.1, 0.3, and 0.5 were defined as small, medium and large.

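### The SAP lets the group-by-time interaction decide effectiveness but names no test of it; the interaction must not be inferred from within-arm tests or Cohen's d grades

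*SAP*

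**What the plan says.** The SAP is a single unnumbered section. Four of its statements matter here.

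- Criterion for effectiveness: "The interaction of group and time determined the effectiveness of mirror therapy on outcome measures". No model, time contrast or interval is given.
- Tests over time: "The paired samples t-test and the Wilcoxin signed rank test were used to analyse within-subject differences (T1 vs T2 vs T3". With three time points this allows three paired contrasts per outcome.
- Tests between arms: "Between-subject differences (MT vs PL) were analysed using the independent samples t-test and the Mann-Whitney U test". The SAP does not say whether these are applied to change or to the scores at each time.
- Level and effect sizes: "All tests were conducted on a 5% significance level", and "Effect sizes for parametric tests were calculated using Cohens's d for within-group analysis and r for between group analysis". For grading, "Cohens d values of 0.2, 0.5, and 0.8 were interpreted as small, medium, and large respectively".

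The reference to within-group effect sizes supports reading the paired tests as run separately in each arm, which gives up to six per outcome. The SAP does not label them descriptive or give them any stated role.

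The Protocol gives the size: "A total of 30 participants will be randomly assigned to one of two conditions". It describes treadmill training for patients in general ("Patients will verbally guide the speed of the treadmill at the beginning of each of the 12 therapy sessions") and the mirror for experimental participants only. Neither document defines T1, T2, T3 or PL.

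**The concern.** The stated criterion and the listed tests do not meet. None of the four tests named for the outcome comparisons (paired t, Wilcoxon, independent t, Mann-Whitney) tests a group-by-time interaction unless the between-arm pair is applied to change scores, and the SAP does not say so. The only analyses explicitly tied to time are the paired ones. An analyst following the text could therefore judge the interaction by whether MT changed significantly and PL did not, or by whether MT earned the higher d grade.

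That comparison sets randomisation aside. Change within MT contains whatever the mirror does, plus training, familiarity with the tests, time and regression to the mean. When two arms share the same true change, chance alone often puts one side of p = 0.05 and the other across it. At stake is a claim of benefit that the randomised comparison does not support. The effect-size plan adds to the risk: within-arm change is graded by d and the between-arm difference by r, so the two cannot be read on one scale.

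**Working it through.** The documents give no power, target effect or SD, so there is no planned figure to reproduce. The check asks how often the within-arm pattern would suggest a mirror effect when there is none.

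**Inputs**
- 30 participants in two conditions (Protocol). The allocation ratio is not stated; 1:1, or n = 15 per arm, is assumed, with 12 per arm as a sensitivity case.
- 5% level (SAP). Sidedness is not stated; two-sided is assumed.
- Normal changes, independent arms, no dropout (assumed).
- Common true change δ, in SDs of change, equal in MT and PL. The documents give no value, so a range is shown.

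**Step 1: power of one paired t-test.** p is the probability that |t| exceeds 2.145 (14 df) under a noncentral t with noncentrality δ√15. For δ = 0.5 the noncentrality is 0.5 × 3.873 = 1.936 and p = 0.438.

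**Step 2: discordance between arms.** P(only MT significant) = p(1 − p). P(exactly one arm significant) = 2p(1 − p). For δ = 0.5: 0.4379 × 0.5621 = 0.246, and twice that is 0.492.

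| δ | p, n = 15 | Only MT | Exactly one arm | Only MT, n = 12 |
|---|---|---|---|---|
| 0.2 | 0.112 | 10% | 20% | 9% |
| 0.5 | 0.438 | 25% | 49% | 23% |
| 0.8 | 0.821 | 15% | 29% | 20% |
| 1.0 | 0.949 | 5% | 10% | 10% |

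At 15 per arm the maximum is 25% for MT alone and 50% for exactly one arm, at δ near 0.54. A simulation of 50,000 trials per setting agreed: 9.7%, 24.8% and 14.5% for MT alone at δ = 0.2, 0.5 and 0.8.

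**Step 3: the direct comparison.** In the same simulations the independent t-test on T1-to-T2 change rejected in 4.8% to 5.0% of trials whatever δ was. Half of the nominal 5%, 2.5%, favours MT.

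**Step 4: several contrasts.** With a common change of 0.5 at both T2 and T3 (between-visit correlation 0.8 assumed), at least one of the three paired contrasts is significant in MT but not in PL in 41% of trials.

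**Step 5: d grades.** Take d as mean change over the SD of change (the SAP does not say which SD it uses) and apply the SAP's cut-offs. With equal true d of 0.35, 0.5 or 0.8, the arms receive different grades in 69%, 70% or 59% of trials, and MT receives the higher one in 34%, 35% or 30%.

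**Step 6: what the direct test can detect.** At 15 per arm its power for a between-arm difference in change of 0.2, 0.5, 0.8 or 1.0 SD of change is 8%, 26%, 56% or 75%.

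**The case against.** The strongest reply is that the SAP already places the efficacy inference where it belongs. It names the interaction as the criterion and plans MT vs PL tests. Nowhere does it adopt significance in MT but not in PL as a rule. The 5% to 25% figures are error rates of a rule that the SAP does not state, and a pilot may properly describe change within each arm. All of that stands. What remains is that the interaction has no test attached, the within-arm tests have no stated role, and the text does not exclude the invalid comparison.

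The size also depends on the common change. MT-only significance peaks near 0.54 SD and falls to 5% at 1.0 SD. The documents do not say which value is plausible, so no single figure should be quoted alone.

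One could also keep the paired tests and only label them descriptive. That would remove most of the risk, but a p-value and a graded d in each arm still invite the comparison, and a mean change with its interval gives the same description.

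A reader might go further and infer three things that the documents do not support:
- *That there is a single baseline and no run-in.* T1 is not defined and the number of baseline assessments is not given.
- *That the T2 to T3 test is a retention test too weak to show a loss.* Neither document mentions retention or says when T2 and T3 fall. Its miss rate would also depend on the SD used and the between-visit correlation, and neither is given.
- *That the comparator is certainly treadmill-trained.* The title and the session text point that way, but PL is never described.

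The point needs none of these. Even with an untrained comparator, within-arm change absorbs practice, time and regression to the mean.

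**Conclusion.** The concern holds as a gap between the SAP's criterion and its listed tests. It does not hold as a charge that the plan judges efficacy by within-arm tests. If the gap were filled by contrasting within-arm significance, MT alone would appear to improve in about 10% (δ = 0.2), 25% (0.5), 15% (0.8) or 5% (1.0) of trials with no mirror effect, against 2.5% in MT's favour for a direct test of the difference in change. Contrasting d grades would favour MT in 30% to 35% of such trials for true d of 0.35 to 0.8. These figures assume 15 per arm, two-sided tests, normal changes, equal true change and no dropout. They were computed for t-tests; the same reasoning applies to the signed rank test. The change is worth making because it is cheap and follows the SAP's own criterion. The gap does not invalidate the trial.

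**What to change.** Amend the SAP in three places.

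1. Define T1, T2, T3 and PL. The next item takes T1 as the pre-treatment assessment, which the SAP should confirm.
2. State the interaction as an estimate: the MT minus PL difference in change from T1, at T2 and at T3, each with a 95% CI. Say that this is the sole basis for any conclusion about mirror therapy. The independent samples t-test already named serves if it is applied to change scores.
3. Replace the paired tests and within-group d grades with mean change and 95% CI in each arm, and state that no conclusion on mirror therapy is drawn from them.

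The cost is wording and the loss of within-arm p-values. No extra data are needed and there is less output to run. The direct comparison will be imprecise at this size (26% power for a difference of 0.5 SD of change), so the interval should lead the report. Within-arm significance cannot make up for that imprecision.

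### Within- and between-group comparisons each have a parametric and a rank test with no rule for which is primary, and no baseline-adjusted between-group analysis is named

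*SAP*

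**What the plan says.** The SAP is one unnumbered section. On distributional checks it says: "Conformity to the normal distribution of variables was tested using a combination of the Shapiro-Wilk test and visual assessment (histograms". It gives no cut-off and no rule for when test and histogram point different ways. It does not say whether the check is made by arm, by visit or on change scores, or what follows from the result.

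Two kinds of comparison then each get a pair of tests joined by the word and:

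- Within arm: "The paired samples t-test and the Wilcoxin signed rank test were used to analyse within-subject differences (T1 vs T2 vs T3".
- Between arms: "Between-subject differences (MT vs PL) were analysed using the independent samples t-test and the Mann-Whitney U test".

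Baseline comparisons are handled differently, with one test per variable type: "Groups were compared at baseline using the independent samples t-test for the continuous variables, and the chi-square test for categorical data".

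On effect sizes, the SAP says "Effect sizes for non-parametric tests were calculated using r". For parametric tests it uses Cohen's d within arm and r between arms.

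The criterion for benefit is stated separately: "The interaction of group and time determined the effectiveness of mirror therapy on outcome measures". No test or model is attached to it. The level is set by "All tests were conducted on a 5% significance level".

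**The concern.** A SAP should settle, before outcome data are seen, which analysis produces the headline result. Here two p-values are available for each follow-up comparison, and nothing ranks them. If the normality check is meant to choose, the method depends on the data and partly on how someone reads a histogram of a small sample. If both tests are run, nothing says what to conclude when they disagree. Within arms the choice also decides whether d or r is reported, and those are judged against different small, medium and large cut-offs.

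A second issue sits beside this. Neither named between-group test adjusts for the baseline value, although the trial measures it. In a trial this small that adjustment bears on how precisely the MT minus PL difference is estimated.

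**Working it through.** **Inputs.** Total size comes from the Protocol: "A total of 30 participants will be randomly assigned to one of two conditions". The allocation ratio is not given, so 30/2 = 15 per arm is an assumption, as is no missing data. The 5% level is in the SAP; two-sided testing is assumed. T1 is taken to be baseline, which the documents do not state. They give no SD, effect size, baseline correlation or power, so there is no planned figure to reproduce. The distributions, effects and correlations below are assumptions.

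**Step 1: what the open choice does to error rates.** Simulation, 20,000 runs per row, 15 per arm, Shapiro-Wilk at 0.05 in each arm. The middle columns are type I error with no true difference. The last two give how often the t-test and Mann-Whitney disagree on significance.

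| Data shape | Shapiro-Wilk rejects in at least one arm | t-test | Mann-Whitney | Pre-test chooses | Either may be claimed | Disagree, no effect | Disagree, shift 0.8 |
|---|---|---|---|---|---|---|---|
| Normal | 9.5% | 5.0% | 4.4% | 5.1% | 5.8% | 2.2% | 7.7% |
| Gamma (shape 4) | 38.6% | 4.9% | 4.5% | 5.4% | 6.0% | 2.5% | 9.8% |
| Lognormal (sigma 0.5) | 62.5% | 4.7% | 4.8% | 5.5% | 6.1% | 2.8% | 14.0% |
| Exponential | 89.3% | 4.8% | 4.6% | 5.1% | 6.3% | 3.1% | 18.5% |
| t, 3 df | 45.4% | 4.3% | 4.4% | 4.7% | 5.5% | 2.4% | 11.6% |

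The shift is in SD units except in the t row, which was not standardised. The pre-test column is a weighted mix. For normal data: 0.905 × 5.03% + 0.095 × 5.48% = 5.07%.

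The check is a weak selector for moderate skew: with gamma data it passes both arms in 100 − 38.6 = 61% of trials. This does little harm to overall error, because the t-test alone already holds its level. The choice matters more when there is an effect, since the two tests then disagree in 8% to 19% of trials.

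**Step 2: effect measures.** Within an arm (n = 15, normal data, true standardised change 0.8), d averages 0.85. Wilcoxon r averages 0.64 computed as Z/√n, or 0.45 as Z/√(2n); the SAP does not say which. On the same data the SAP's size labels for d and r differ in 38% or 20% of trials respectively. Between arms the measure is r for either test. Values from t and from Z differ by about 0.03 on average with normal data, and fall in different bands in 15% to 18% of trials.

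**Step 3: baseline adjustment.** Let the outcome SD be 1, the effect 0.5 and the baseline correlation ρ. The noncentrality is (0.5/s)/√(2/15), where s is the SD each analysis works with:

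- Follow-up value: s = 1.
- Change score: s = √(2(1 − ρ)).
- ANCOVA: s = √(1 − ρ²).

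| Analysis | ρ | s | 0.5/s | Noncentrality | Power |
|---|---|---|---|---|---|
| t-test, follow-up | any | 1 | 0.500 | 1.37 | 26% |
| t-test, change | 0.6 | 0.894 | 0.559 | 1.53 | 32% |
| t-test, change | 0.8 | 0.632 | 0.791 | 2.17 | 55% |
| ANCOVA | 0.6 | 0.800 | 0.625 | 1.71 | 37% |
| ANCOVA | 0.8 | 0.600 | 0.833 | 2.28 | 58% |

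The ANCOVA powers are simulated; the formula alone, with 27 df, gives 38% and 60% because it ignores chance baseline imbalance. Simulation runs at ρ = 0.6 ranged over 31% to 33% for change and 37% to 38% for ANCOVA. Mann-Whitney on follow-up values has about 24%. Simulated ANCOVA type I error is about 5% with normal data.

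In variance terms ANCOVA is never worse than change scores: 2(1 − ρ) − (1 − ρ²) = (1 − ρ)², which cannot be negative.

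**The case against.** The strongest reply is that listing a t-test and a rank test is ordinary shorthand, that the consequences are slight, and that preferring ANCOVA is partly taste. Much of this stands, and several stronger readings fail.

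- A reader might infer that every comparison has two tests. Baseline comparisons have one fixed test per variable type, and the group-by-time criterion has none.
- A reader might infer that the normality test picks the method. That is plausible but unwritten; the text equally allows both tests to be run. What can be shown is that no rule is stated.
- A reader might infer that the 5% level is seriously breached. A choosing pre-test stays within 4.7% to 5.5%. The figure of about 6% needs an analyst free to claim either result, which the SAP does not describe.
- A reader might infer that the between-group effect measure switches with the test. It is r in both cases; only the within-arm measure changes.
- A reader might infer that the plan ignores baseline and that ANCOVA is far more powerful than anything listed. The paired tests use T1, and the SAP does not say whether the between-group tests use follow-up values or change. Against follow-up values the ANCOVA gain is 11 to 32 points (37 − 26, 58 − 26). Against change scores it is 5 to 3 points (37 − 32, 58 − 55).

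What survives is that no primary test is named for either kind of follow-up comparison, and that a baseline-adjusted analysis is available at almost no cost.

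**Conclusion.** The point holds for the within- and between-group comparisons. It is mainly a failure to pre-specify, and only slightly an error-rate problem: at worst 6.3% in the scenarios examined. The practical stake is that the two tests would lead to different significance calls in 8% to 19% of trials with a 0.8 shift, with nothing in the SAP to settle which call counts.

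At the correlations examined, ANCOVA gains over either reading of the between-group t-test. The size of the gain depends on which reading was intended. All figures rest on 15 per arm, complete data, two-sided testing, T1 as baseline, and the assumed data shapes, effects and correlations. The change is worth making because it is cheap and also gives a method to the effectiveness criterion, which at present has none.

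**What to change.** For each continuous outcome, name ANCOVA of the follow-up value on arm and the T1 value as the single main between-group analysis. Choose T2 or T3 as the primary time point in advance and label the other secondary. Report the adjusted MT minus PL difference with a 95% CI.

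State that this contrast is the group-by-time criterion for effectiveness. It can serve as such because subtracting T1 from the outcome, with T1 still a covariate, leaves the arm coefficient unchanged; the estimate is therefore also the adjusted difference in change.

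Keep Shapiro-Wilk and histograms as description, with no role in choosing a test. Present rank tests as a labelled sensitivity analysis that cannot replace the main result. Within arms, fix one effect measure in advance.

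The cost is a few sentences of SAP text, one model per outcome and time point, and one degree of freedom for the covariate. The downside is that the analyst can no longer make a rank test the headline result when the data look skewed.

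### The SAP lets the group-by-time interaction decide effectiveness but ties no test or deciding visit to it, and does not use the baseline value as a covariate

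*SAP*

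**What the plan says.** The SAP is one unnumbered section. Its only decision rule for efficacy is that "The interaction of group and time determined the effectiveness of mirror therapy on outcome measures".

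It names two sets of outcome tests. Within subjects, the paired t-test and the Wilcoxon signed rank test "were used to analyse within-subject differences (T1 vs T2 vs T3"). Between arms, "Between-subject differences (MT vs PL) were analysed using the independent samples t-test and the Mann-Whitney U test". It does not say whether the between-arm tests are applied to follow-up values or to changes from T1. No change score, ANCOVA, repeated-measures ANOVA or mixed model is mentioned, and no confidence interval is planned.

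On baseline, the SAP says "Groups were compared at baseline using the independent samples t-test for the continuous variables" and does not mention adjustment. The level is set by "All tests were conducted on a 5% significance level". On missing values, "patients were excluded from a given analysis if their corresponding measurement was missing".

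The Protocol has no analysis text that fills these gaps. It gives the size ("A total of 30 participants will be randomly assigned to one of two conditions") and shows that baseline measurements exist, since treadmill speed is "guided by baseline data from the Ten Metre Walk Test".

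**The concern.** A decision rule needs a statistic. With three visits, a group-by-time interaction could mean the between-arm difference in change from T1 to T2, the same from T1 to T3, or the joint test on two degrees of freedom. Each fits the SAP's sentence, and on the same data they can give different answers. Because none is named, the choice can be made after the results are seen, and the nominal 5% no longer describes the procedure.

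The second, smaller matter is efficiency. In a trial of 30 patients, the baseline value of the outcome is the most obvious source of extra precision. The plan does not use it as a covariate.

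**Working it through.** **Stated figure.** The only design figure is the total of 30. It cannot be reproduced, because the documents give no power, target effect or SD.

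**Inputs.** From the documents: 30 patients, two arms, three time points, 5% level. Assumed, because the documents are silent: 15 per arm, two-sided tests, T1 = baseline, normal data, no missing values, equal correlation ρ between visits of 0.3, 0.5, 0.7 or 0.9, and a true effect of 0.5 SD at both follow-up visits. Simulations use 40,000 trials per setting.

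**Step 1. Can the listed tests deliver the interaction?** Yes, if applied to change. The interaction over two visits is (mean change in MT) − (mean change in PL), and an independent t-test on change tests exactly that. The SAP does not say the test is used this way, and two such contrasts would still be open.

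**Step 2. False positives when the contrast is open.** With equal correlations, the covariance of (T2 − T1) and (T3 − T1) is ρ − ρ − ρ + 1 = 1 − ρ, and each variance is 2(1 − ρ). The correlation between the two changes is therefore 0.5 whatever ρ is, so the inflation hardly depends on the assumed value. For comparison, two independent tests would give 1 − 0.95² = 9.75%.

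| No true effect, simulated | ρ = 0.3 | 0.5 | 0.7 | 0.9 |
|---|---|---|---|---|
| One named change contrast (T1–T2) | 5.0% | 5.0% | 4.8% | 5.2% |
| Either change contrast | 9.1% | 9.0% | 9.1% | 9.2% |
| Either contrast or the joint 2-df test | 10.0% | 9.8% | 10.0% | 10.0% |
| ANCOVA at T2 only | 5.0% | 5.0% | 4.9% | 5.2% |
| ANCOVA at either T2 or T3 | 9.6% | 9.4% | 9.4% | 9.2% |

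The last two rows show that ANCOVA does not cure this. Naming one visit does, under either model.

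**Step 3. Precision.** In units of the outcome variance, the follow-up value alone has variance 1, change has 2(1 − ρ), and the baseline-adjusted value has 1 − ρ². The ratio of change to adjusted is 2(1 − ρ)/(1 − ρ²) = 2/(1 + ρ), which is 1.54, 1.33, 1.18 and 1.05.

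The 95% CI half-width is t × √(2/15) × SD. At ρ = 0.5, change gives 2.048 × 0.365 × 1.000 = 0.75 SD (28 df), and ANCOVA gives 2.052 × 0.365 × 0.866 = 0.65 SD (27 df). The table shows these values by formula. For ANCOVA the formula leaves out chance baseline imbalance, and the simulated mean half-widths are slightly larger: 0.72, 0.66, 0.54 and 0.33 SD.

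| True effect 0.5 SD | ρ = 0.3 | 0.5 | 0.7 | 0.9 |
|---|---|---|---|---|
| Power, change from T1 | 20% | 26% | 40% | 84% |
| Power, ANCOVA on T1 | 28% | 32% | 45% | 84% |
| Half-width, change (SD) | 0.89 | 0.75 | 0.58 | 0.33 |
| Half-width, ANCOVA (SD) | 0.71 | 0.65 | 0.54 | 0.33 |

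Power is simulated. The noncentral t distribution gives 20.1/26.2/40.0/84.0% for change. Power on the T2 value alone is about 26% throughout.

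**Step 4. Does the visit matter to the verdict?** With the same 0.5 SD effect at both visits, the two change contrasts disagree on significance in 23/27/33/20% of trials. Two ANCOVAs, at T2 and at T3, disagree in about 35/35/37/20%. The cause is two visits and low power, not the choice of model.

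**The case against.** The strongest reply is that the sponsor probably meant the between-arm tests to be run on change from T1. That reading makes the plan coherent: the test is valid, it takes T1 into account by subtraction, and the planned effect size r belongs to it. The minimal correction would then be to say so and name the visit, with ANCOVA an optional refinement. Most of this stands. The SAP does not state that reading, however, and even on it the choice between T2 and T3 stays open.

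Four stronger readings are tempting, and the documents do not support them.

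- *The analysis is biased because it ignores baseline.* The arms are randomised, so comparing follow-up values is valid too, although it is not the stated criterion. Any test of the interaction already subtracts T1.
- *Baseline serves only to compare the arms at entry.* If T1 is baseline, it also enters the paired tests and the interaction. What is missing is its use as a covariate.
- *The trial's error rate is 9%.* That figure assumes the favourable contrast is always picked. It shows what the text allows, not what was done.
- *Disagreement between visits shows that ANCOVA is needed.* ANCOVA results disagree between visits at least as often, so this argues for naming a visit and for nothing more.

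The pilot label is a fair plea in mitigation. It does not remove the point, because the SAP itself sets a criterion of effectiveness and tests it at 5%.

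**Conclusion.** The point holds as a gap in specification with a modest efficiency loss beside it. The sole criterion of effectiveness has no test and no deciding visit. The cost is a false-positive rate per outcome of up to about 9% if either change contrast may decide, or about 10% if the joint test may too. This result is nearly independent of the correlation under the equal-correlation assumption. It does not count multiplicity across outcomes, which is a separate matter.

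The covariate point is one of precision. The power gain over change is about 8, 6, 5 and 0 percentage points at correlations of 0.3, 0.5, 0.7 and 0.9. These figures rest on an assumed effect, assumed correlations, 15 per arm, normal data and complete follow-up, none of which the documents give. At high correlation the choice between ANCOVA and change hardly matters.

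This should be fixed. It does not invalidate the trial, and the pilot status tempers it further.

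**What to change.** Amend the SAP as follows.

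1. Define T1, T2 and T3.
2. Have the sponsor name one deciding follow-up visit, T2 or T3, to match the trial's aim. The other visit and any joint interaction test become secondary.
3. For each outcome, make the deciding analysis the MT minus PL difference at that visit from ANCOVA on group and T1 value, reported with its 95% CI and p-value.
4. For outcomes listed in advance as clearly non-normal, use the Mann-Whitney test on change from T1 to the same visit, with the planned effect size r. Fix that list before outcome data are seen.
5. Label the within-arm paired tests descriptive. The decision rule already implies this, so it is a clarification only.

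The step that restores the 5% level is the second, together with one named analysis. ANCOVA adds the precision.

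The cost is a few lines of text and one model per outcome. No extra patients or visits are needed: both documents already refer to baseline measurements. One caution applies: the SAP is written in the past tense and the Protocol mainly in the future tense, so it is unclear whether data had been analysed. If they had, new text cannot undo a choice already made, and the ANCOVA must be reported as post hoc.

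### Does grading within-arm change on d and the MT–PL effect on r make the SAP's effect-size labels unsound?

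*SAP*

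**What the plan says.** The SAP is one unnumbered section. For parametric tests it says: "Effect sizes for parametric tests were calculated using Cohens's d for within-group analysis and r for between group analysis". For rank tests, within or between arms, it says: "Effect sizes for non-parametric tests were calculated using r". The labels are then fixed: "Cohens d values of 0.2, 0.5, and 0.8 were interpreted as small, medium, and large respectively", and "r values of 0.1, 0.3, and 0.5 were defined as small, medium and large".

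The comparison of arms is described as follows: "Between-subject differences (MT vs PL) were analysed using the independent samples t-test and the Mann-Whitney U test". The judgement on efficacy is placed elsewhere: "The interaction of group and time determined the effectiveness of mirror therapy on outcome measures". The Protocol gives the size: "A total of 30 participants will be randomly assigned to one of two conditions".

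Neither document gives a formula for r, the SD used in d, an allocation ratio, or a conversion between the two scales.

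**The concern.** For one parametric outcome, a report would carry two labels from the same three words: one for change within the mirror-therapy arm, on d, and one for MT against PL, on r. A reader will tend to take *medium* to mean the same in both places. If the r cut-offs are harder to reach, the randomised comparison is graded more strictly than uncontrolled change within an arm. The SAP names no confidence interval, so beyond means, SDs and p-values these labels are its only stated way to convey the size of an effect. At stake is whether readers could be misled about how the controlled effect compares with the uncontrolled one.

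**Working it through.** **Inputs.** From the SAP: d cut-offs 0.2/0.5/0.8 and r cut-offs 0.1/0.3/0.5. From the Protocol: 30 participants, two arms. Assumed, because not stated: allocation 15 v 15 (20 v 10 as an extreme), and one of two common formulas for r. The plan states no conversion, so there is no figure of its own to reproduce.

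**1. Converting r to d.** For two arms, t = d·√(n₁n₂/(n₁+n₂)); at 15 v 15 the multiplier is √7.5 = 2.739.

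- Formula 1, r = √(t²/(t²+df)) with df = 28, so t = r·√28/√(1−r²). At r = 0.3, t = 1.664 and d = 1.664/2.739 = 0.608. At r = 0.5, t = 3.055 and d = 1.116. At r = 0.1, d = 0.194.
- Formula 2, r = t/√N with N = 30, so d = r·√30/2.739 = 2r, giving 0.200/0.600/1.000.
- At 20 v 10: 0.206/0.645/1.183 (formula 1) and 0.212/0.636/1.061 (formula 2).

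*Small* coincides with d = 0.2. *Medium* and *large* do not coincide with 0.5 and 0.8 under any variant.

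**2. How often an estimate falls where the scales disagree.** The bands are d from 0.5 to the *medium* bar and from 0.8 to the *large* bar, either sign (noncentral t, 28 df). With formula 1 the chance is 27%, 38% and 11% at true d of 0.5, 0.8 and 0. With formula 2 it is about 22%, 28% and 10%.

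**3. Do within-arm and MT–PL labels then disagree more?** Simulation: 400,000 trials, 15 per arm, normal change scores with SD 1, both effects standardised by the SD of change, formula 1. *Created* means the labels agree on a single d but differ under the SAP. *Removed* means the reverse.

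| True change MT, PL | Created | Removed | Differ, single d | Differ, SAP mix | Net (points) |
|---|---|---|---|---|---|
| 0.5, 0 | 11.2% | 12.6% | 53.7% | 52.3% | −1.4 |
| 0.8, 0 | 23.6% | 11.2% | 41.7% | 54.2% | +12.5 |
| 0.8, 0.3 | 18.1% | 2.9% | 65.4% | 80.7% | +15.3 |
| 0, 0 | 1.2% | 5.3% | 52.0% | 48.6% | −3.4 |

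Created counts only the *medium* and *large* bands. The slight offset at *small* (0.194 against 0.2) and simulation error explain why created minus removed is not exactly the net figure. Looking only at created disagreements overstates the effect. Even on one metric the labels differ in 42–65% of trials, because change within an arm and the difference between arms are different quantities.

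**4. Direction.** The SAP does not say whether each effect is scaled by the SD of raw scores or of change. Their ratio is f = √(2(1−ρ)), with ρ the T1–T2 correlation (assumed range). If MT–PL is analysed on change scores and within-arm d uses the raw SD, the formula 1 bars in raw-SD units are 0.608f and 1.116f:

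- ρ = 0.3: 0.72/1.32
- ρ = 0.5: 0.61/1.12
- ρ = 0.7: 0.47/0.86
- ρ = 0.9: 0.27/0.50

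The MT–PL label becomes the more generous one above ρ = 1 − (0.5/0.608)²/2 = 0.66 for *medium* and 1 − (0.8/1.116)²/2 = 0.74 for *large*. No consistent tilt for or against mirror therapy can be shown.

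**5. Size against sampling error.** The 95% half-width for the MT–PL difference at 15 v 15 is 0.748 SD of the analysed score (t quantile with 28 df times √(2/15)). The bars move by 0.608 − 0.5 = 0.108 and 1.116 − 0.8 = 0.316, both well inside that.

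**6. What the alternative would do.** Under the SAP, MT–PL effects are on r for both the t-test and Mann-Whitney. With d for t-test outcomes and r kept for rank tests, the same comparison would be graded at 0.2/0.5/0.8 for some outcomes and 0.1/0.3/0.5 for others.

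**The case for a change.** The strongest case for a change is that the mismatch holds under every formula and split tried, that it touches the only randomised comparison, that an estimate at true d = 0.8 has up to a 38% chance of landing in a mismatched band, and that better wording needs no new data. That each cut-off set is conventional does not answer this, since the complaint is about using both with the same words. A reader also cannot convert between the scales from the SAP alone, because neither the r formula nor the standardiser is given.

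The non-equivalence stands, and so does the missing detail. Three parts do not carry through. First, moving to d is not free: unless labels are dropped altogether, it shifts the inconsistency into the MT–PL results. Second, agreement between a within-arm label and a between-arm label is not something a plan needs to secure, and one metric would not secure it. Third, the reader is not stranded: outcomes are to be described by mean and SD, and if that is done by arm and time point, as is usual, a d on the raw SD can be computed for both contrasts. An MT–PL difference in original units with a 95% interval would be a welcome reporting addition, but it corrects no faulty rule.

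**Conclusion.** The observation is correct but calls for no change. Assuming 15 v 15 and a standard r formula, *medium* and *large* on r correspond to a between-arm d of about 0.60–0.61 and 1.00–1.12, against 0.5 and 0.8 on d. The consequence is confined to descriptive wording: the 5% tests and the group-by-time criterion for effectiveness do not use the labels. The net effect on label agreement runs from about 3 points better to about 15 points worse than a single d (formula 1, both effects on the SD of change), and the direction of any leniency depends on standardisers and a correlation that the documents do not give. Using r for all between-arm results is a fair trade-off, because it keeps t-test and Mann-Whitney outcomes on one scale. The r formula and the SD behind d are a gap that analysts ordinarily fill by stating them beside the results.
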